2.2 Intervention

2.2.1 Internet-delivered Mindfulness Based Training (iMBT)

The iMBT developed for this study will be adapted from our team's previous study³ and the manual of mindfulness based cognitive therapy⁴. To suit a public mental health approach and to increase program attractiveness and adherence, the program is designed to be brief in nature while strive to preserve all the essential elements in the original manual and program, for example, participants will be asked to practice meditations for 15 minutes a day instead of the original 45 minutes a day, and each module is shortened to approximately 1 hour instead of the original 2.5 hours.

The core focus of iMBT will be on educating participants to adopt a new way of being and relating to their thoughts and feelings, and altering specific cognitions is not emphasized. This iMBT is comprised of six weekly modules on education about mindfulness, guidance on using mindfulness skills to manage symptoms, guided meditations (e.g., mindful breathing, mindful eating, mindful walking, body scan, acceptance, choiceless awareness and disengaging from thoughts exercise), and guidance on using informal mindfulness skills in day-to-day life.

Readings, audio and graphics are included to explain the concept of mindfulness and overcome common difficulties associated with mindfulness practice. Furthermore, participants are encouraged to practice daily mindfulness exercises using the downloadable audio built within the learning platform. Participants will reflect on their experiences by keeping a personal log. An online coach, who will be a trained undergraduate student in

psychology, will give weekly written feedback based on this log through a secured e-mail system, guiding the participants through the program with personal feedback, encouragement and support.

2.2.2 Treatment-as-usual control group (TAU)

The TAU group will be advised to seek assistance from their usual healthcare provider when needed.

2.3 Power Calculation and Sample Size

Based on past research⁵, we expected a small to medium ($f = 0.11$) difference between the iMBT and the TAU control group. Thus, using G * Power software (version 3.1.9.2), a sample size of 116 will be needed to detect superiority of the intervention groups over the TAU control group with 80% power.

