Participants who have provided consent and passed an online screening (based on the above-mentioned inclusion and exclusion criteria) will engage in a 6-week IMBT, consisting of 6 modules with 4 sections each. It is expected that participants will complete one module per week, each module lasting around 1 hour while participants are encouraged to practice for 15 minutes a day. The control group will be advised to seek assistance from their usual healthcare provider when needed.

Both treatment group and control group will be assessed at four different time points: before intervention (T0), (2) 2,4 weeks since the commencement of group (T1,2), (3) 6 weeks after (i.e., when the intervention ends) (T3), (4) at 3-month follow-up(T4).

Initial screening will utilise the PHQ9. Once participants have been recruited, online assessments will be conducted via Qualtrics at each of the aforementioned timepoints. The assessments will include:

- Patient Health Questionnaire (PHQ9)
- Five Facets Mindfulness Questionnaire – Short form (FFMQ-SF)
- Warwick Edinburgh Mental Wellbeing Scale
- Credibility and Expectancy Questionnaire (CEQ)
- Difficulties in Emotional Regulation Scale (DERS)
- Nonattachment scale
- Stillness scale
- Equanimity scale
- Peace of mind scale

5. Will consent form be used? Yes No

If No, please provide reason(s) below:

(a) Type of consent (*Check all that apply*)(Please attach a copy of consent form.)

Formal Consent

- Informed consent
(for participants able to give legal valid informed consent and not belonging to any vulnerable groups)
- Parent/guardian consent
(for participants under 18 years old or those belonging to a vulnerable group)
- Assent form
(for participants not competent to give legal valid informed consent)
- Passive informed consent
(for surveys to be conducted through the schools or other authorities)

Informal Consent

Please provide justifications:

6. Confidentiality of data

(a) Collection of auditory and visual data (*Check all that apply*)

- Audiotapes
- Videotapes
- Still photos
- Not applicable

(b) Does the study involve multi-phase data collection? Yes No

If Yes, please explain the tracking and coding system(s):

Participants will be identified by a unique ID to match their data across time.

- (c) Does the study involve collecting data through an Internet survey platform? Yes No

If Yes, please address the confidentiality of data collected via e-mail, Web interfaces, and other networked information:

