1.3 Aims and hypotheses

The research goals of this randomized controlled trial are to determine the feasibility and the mechanism of change of iMBT that has been developed using the Acceptance Checklist for Clinical Effectiveness Pilot Trials (ACCEPT) framework³⁵.

The primary research question is as follows:

- What is the effectiveness of the iMBT in relation to improvements on depressive symptoms among people with clinical depression, relative to a usual care control after the intervention and in 3-month follow-up?

Secondary questions include the following:

- Which facet(s) of mindfulness (i.e., observe, describe, act with awareness, non-react and non-judgement) improved during the intervention?
- How does the growth trajectory of different facets of mindfulness relate to the improvement of well-being and reduction of ill-being?

We hypothesize that:

- H1 Participants in iMBT group will have greater reduction in depressive symptoms and increase in all facets of mindfulness and mental well-being, than the usual care group at post-intervention, and 3-month follow-up.
- H2 Using latent growth analysis, the intraindividual growth trajectory of the monitor and acceptance facets of mindfulness would mediate the effect of iMBT on the intraindividual changes in depressive symptoms.
- H3 Using multi-group analysis, in accord with Acceptance and Monitor theory, the relationship between the growth trajectory of monitor facets of mindfulness and the growth trajectory of depressive symptoms will be moderated by the level of acceptance. People with greater acceptance of inner experience will benefit more from the change of monitor facets of mindfulness in iMBT.

References

1. FerrariAJ, SomervilleAJ, BaxterAJ, et al. Global variation in the prevalence and incidence of major depressive disorder: A systematic review of the epidemiological literature. *Psychol Med*. 2013. doi:10.1017/S0033291712001511
2. LiuQ, HeH, YangJ, FengX, ZhaoF, LyuJ. Changes in the global burden of depression from 1990 to 2017: Findings from the Global Burden of Disease study. *J Psychiatr Res*. 2019. doi:10.1016/j.jpsychires.2019.08.002
3. PatelV, ChisholmD, ParikhR, et al. Addressing the burden of mental, neurological, and substance use disorders: Key messages from Disease Control Priorities, 3rd edition. *Lancet*. 2016. doi:10.1016/S0140-6736(15)00390-6

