2.4 Analytical procedure

2.4.1 Efficacy analyses of iMBT on Depressive symptoms, Mindfulness, and Mental Well-being

Significance testing of baseline group equivalence will be conducted using Analysis of variance (ANOVA) and chi square test if the variables consisted of nominal data.

To investigate the efficacy of iMBT, intention-to-treat (ITT) linear mixed models using restricted maximum likelihood (REML) estimation will be conducted for each outcome measure.

Fixed factors of time, group, and time*group will be entered in each model. Within-group effect size will be computed for pre(T0)-to-post(T3), and pre(T0) to follow-up(T4) changes on each outcome measures, and between-group effect sizes (Hedge's g) will be computed at post(T3) and follow-up(T4). Reliable change scores were calculated⁶ between pre(T0)and post(T3)-intervention, as well as between pre(T0)and follow-up(T4) for the PHQ-9, to determine rates of clinically reliable improvement and deterioration. All analyses will be performed in SPSS version 24.

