2.5 Feasibility

Given that our laboratory has already developed the prototype of the iMBT, it is anticipated that this trial will be completed within a 2-year period, with approximately 70% of participants retained. This is in line with similar e-psychotherapy studies where one meta-analysis reported an average of 23% dropout.

References

1. SchulzKF, AltmanDC, MoherD. CONSORT 2010 Statement: Updated guidelines for reporting parallel group randomised trials. *Ital J Public Health*. 2010. doi:10.4178/epih/e2014029
2. SheehanDV., LecrubierY, SheehanKH, et al. The Mini-International Neuropsychiatric Interview (M.I.N.I.): The development and validation of a structured diagnostic psychiatric interview for DSM-IV and ICD-10. In: *Journal of Clinical Psychiatry*. ; 1998.
3. MakWWS, TongACY, YipSYC, et al. Efficacy and moderation of mobile app–Based programs for mindfulness-Based training, self-Compassion training, and cognitive behavioral psychoeducation on mental health: Randomized controlled noninferiority trial. *J Med Internet Res*. 2018. doi:10.2196/mental.8597
4. StoneAB. Mindfulness-Based Cognitive Therapy for Depression: A New Approach to Preventing Relapse. *Psychiatr Serv*. 2005. doi:10.1176/appi.ps.56.9.1165
5. SpijkermanMPJ, PotsWTM, BohlmeijerET. Effectiveness of online mindfulness-based interventions in improving mental health: A review and meta-analysis of randomised controlled trials. *Clin Psychol Rev*. 2016. doi:10.1016/j.cpr.2016.03.009
6. JacobsonNS, TruaxP. Clinical Significance: A Statistical Approach to Defining Meaningful Change in Psychotherapy Research. *J Consult Clin Psychol*. 1991. doi:10.1037/0022-006X.59.1.12
7. ByrneBM. *Structural Equation Modeling with AMOS: Basic Concepts, Applications, and Programming, Second Edition.*; 2013. doi:10.4324/9780203805534
8. DuncanTE. *An Introduction to Latent Variable Growth Curve Modeling.*; 2013. doi:10.4324/9780203879962
9. MacKinnonDP, LockwoodCM, WilliamsJ. Confidence limits for the indirect effect: Distribution of the product and resampling methods. *Multivariate Behav Res*. 2004. doi:10.1207/s15327906mbr3901_4
10. HuLT, BentlerPM. Cutoff criteria for fit indexes in covariance structure analysis: Conventional criteria versus new alternatives. *Struct Equ Model*. 1999. doi:10.1080/10705519909540118

7. Working Schedule

- | | | |
|---------------------------------|----------------------|--------------|
| a) Start Date: | June 30, 2020 | (DD/MM/YYYY) |

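### Section 2.3 words f = 0.11 as an iMBT–TAU difference with 80% power at N = 116; read that way, power is about 22% at one time point, whereas 116 is closely reproduced by a group-by-time interaction effect that 2.3 does not name

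*Protocol*

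**What the plan says.** Section 2.3 (Power Calculation and Sample Size) gives the effect as "we expected a small to medium ($f = 0.11$) difference between the iMBT and the TAU control group" and concludes that "a sample size of 116 will be needed to detect superiority of the intervention groups over the TAU control group with 80% power". It names G*Power as the software. It does not name the test, and it mentions no interaction.

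Section 2.4.1 plans an intention-to-treat linear mixed model (REML) for each outcome: "Fixed factors of time, group, and time*group will be entered in each model". It adds that "between-group effect sizes (Hedge's g) will be computed at post(T3) and follow-up(T4)". The primary question in section 1.3 is the effect on depressive symptoms "relative to a usual care control after the intervention and in 3-month follow-up".

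Section 2.5 says "it is anticipated that this trial will be completed within a 2-year period, with approximately 70% of participants retained", and compares this with similar studies, of which "one meta-analysis reported an average of 23% dropout". Section 2.3 does not say whether 116 allows for such loss.

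**The concern.** An f described as a difference between two arms is read as a between-group effect, and for two equal groups it converts directly to a standardised mean difference. A reader of 2.3 will therefore take d = 0.22 as the planned effect and believe that 116 participants give 80% power for it.

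The trial will report exactly that kind of quantity, a between-group Hedges' g at T3 and T4. If the power calculation was in fact run on an interaction effect, f = 0.11 stands for a much larger difference at T3. A non-significant g of around 0.2 would then be read as failure to confirm an effect the trial was powered for, although it had little chance of detecting one that small.

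**Working it through.** **Inputs from the protocol.** f = 0.11, N = 116, power 80% (2.3); 1:1 allocation, so 58 per arm (2.1); time, group and time*group in the model (2.4.1); about 70% retention (2.5).

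**Assumed, because 2.3 does not give them.** Alpha 0.05 (two-sided t or F test); m measurements from 2 to 5; equal correlation r between occasions, from 0 to 0.7; sphericity (epsilon = 1).

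**1. Reproducing 116 as an interaction effect.** Repeated-measures F test, within-between interaction: λ = f²·N·m/(1 − r), df = (m − 1) and (N − 2)(m − 1).
- m = 4, r = 0.5, N = 116: λ = 0.0121 × 116 × 4/0.5 = 11.23, df 3 and 342, power 80.8%.
- The smallest even N with 80% power is 114. The stated 116 is within 2% of it.
- The match depends on the inputs. At r = 0.5, N is 166, 136, 114 and 100 for m = 2, 3, 4 and 5. Exactly 80% at N = 116 needs r of about 0.65, 0.57, 0.49 and 0.42 respectively.

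**2. Trying 116 as a between-group difference.** d = 2f = 0.22.
- One time point: λ = f²·N = 0.0121 × 116 = 1.40, df 1 and 114, power 21.7%. For 80% power N = 652.
- Group effect averaged over m occasions: λ = f²·N·m/(1 + (m − 1)r), df 1 and N − 2.

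| m | r | Power at 116 | N for 80% |
|---|---|---|---|
| 4 | 0.3 | 39.9% | 312 |
| 4 | 0.5 | 31.8% | 408 |
| 4 | 0.7 | 26.6% | 506 |
| 5 | 0.3 | 42.5% | 288 |
| 5 | 0.5 | 32.9% | 392 |
| 5 | 0.7 | 27.1% | 496 |
| 5 | 0 | 74.8% | 132 |

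The last row is the most favourable case tried, and it still falls short of 80% at 116. A one-sided test at a single time point gives 32%.

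**3. What an interaction f of 0.11 means at T3.** With SD 1 and between-group differences d_t at each occasion, f² = mean[(d_t − mean d)²]/4. Solving for the T3 difference:
- pre-post only (m = 2): 0.11/0.25 = 0.44
- m = 3, full effect from the second visit: 0.47
- m = 4, full effect from the second visit: 0.51; linear divergence: 0.59
- m = 5, full effect from the second visit: 0.55; linear to T3, then held: 0.57
- m = 5, linear to T3, then halved at T4: 0.66

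Each is at least 0.44/0.22 = 2 times the literal reading. Conversely, if the true T3 difference is 0.22 SD, the time*group test at N = 116 has about 11–33% power over these shapes with r = 0.3–0.7.

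**4. T3 difference detectable with 80% power** (two-sample t test): 0.525 SD, about 0.53, with 58 per arm. With 70% retention, 0.70 × 116 = 81.2, taken as 82 or 41 per arm: 0.63 SD. The T0–T3 time*group contrast multiplies these by √(2(1 − r)). At r = 0.5 the factor is 1, so nothing changes; at r = 0.3 it is 1.18, giving 0.62 and 0.74.

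**5. Loss to follow-up on the interaction reading.** With 82 completers, m = 4 and r = 0.5, power is 64%. With m = 5 and r = 0.6 the required N is 82, and 82/0.70 = 117, so an allowance could already be included. Section 2.3 does not let the reader tell which. These are complete-case figures and so conservative for the mixed model.

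**The case against.** The strongest reply is that nothing has been shown to be miscalculated. The planned model carries the treatment effect in its time*group term, such a term is often described in words as a difference between arms, and an interaction calculation returns almost exactly 116. The legend to Figure 2 labels T0 to T3 as weeks 0, 2, 4 and 6, which gives some support to four measurements. The description of f as small to medium also suits a T3 difference of 0.44–0.59 SD better than one of 0.22. Alpha, correlation and epsilon may stand in a statistical analysis plan that is not at hand.

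Most of this stands. The interaction reading is the more plausible one, and the absence of those inputs would not by itself be a finding. A reader might infer that 116 is wrong, or that the trial has only 22% power. The documents do not support either statement: the 22% belongs to the literal wording, not to the calculation that was probably run.

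What the reply does not remove is that 2.3 ties the number and the power to an effect from which they do not follow, while 2.4.1 reports results on the scale that the wording suggests.

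Two further inferences should be resisted. A smaller, baseline-adjusted detectable difference cannot be claimed, because the planned model has no baseline covariate; baseline is a level of time. Nor is it established that dropout was ignored; the text is silent.

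**Conclusion.** The point holds as a mislabelled effect size and power claim, and should be fixed. That the figures disagree as worded is firm: no between-group version tried (2–5 occasions, r from 0 to 0.7) reaches 80% at 116. That an interaction effect was entered is likely but not documented; it rests on m = 4, r = 0.5, epsilon 1 and alpha 0.05. The size of the possible misreading is at least a factor of two in the T3 difference, and its exact value depends on the assumed trajectory. The trial is not shown to be undersized for the interaction effect if all 116 contribute. With four measurements and r = 0.5 there is no room for loss.

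As a side note, outside the power defect: the Summary of Research Procedures says "Both treatment group and control group will be assessed at four different time points" but lists T0 to T4, which is five.

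**What to change.** Keep N = 116 and reword section 2.3.

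1. If an interaction effect was entered, say so and limit the 80% claim to it, for example: *With 116 participants the trial has 80% power for a group-by-time interaction effect of f = 0.11 (G*Power, repeated measures, within-between interaction; alpha [ ], [ ] measurements out of T0–T4, correlation [ ], epsilon [ ]).* If a between-group f was meant, restate its power as well below 80%, about 22% at a single time point.
2. Add the scale on which results will be reported: *80% power corresponds to a T3 between-group difference of about 0.53 SD with 58 per arm, and about 0.63 SD with 41 completers per arm (complete-case, conservative for the mixed model).* Do not add baseline-adjusted values unless the model gains a baseline covariate.
3. State whether 116 includes the roughly 30% loss expected in 2.5.
4. Separately, reconcile the count of four time points with the five listed.

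The cost is retrieving the G*Power inputs and rewriting one paragraph. The stated sensitivity will look less favourable. Design, sample size and analysis do not change.

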2.4 Analytical procedure

2.4.1 Efficacy analyses of iMBT on Depressive symptoms, Mindfulness, and Mental Well-being

Significance testing of baseline group equivalence will be conducted using Analysis of variance (ANOVA) and chi square test if the variables consisted of nominal data.

To investigate the efficacy of iMBT, intention-to-treat (ITT) linear mixed models using restricted maximum likelihood (REML) estimation will be conducted for each outcome measure.

Fixed factors of time, group, and time*group will be entered in each model. Within-group effect size will be computed for pre(T0)-to-post(T3), and pre(T0) to follow-up(T4) changes on each outcome measures, and between-group effect sizes (Hedge's g) will be computed at post(T3) and follow-up(T4). Reliable change scores were calculated⁶ between pre(T0)and post(T3)-intervention, as well as between pre(T0)and follow-up(T4) for the PHQ-9, to determine rates of clinically reliable improvement and deterioration. All analyses will be performed in SPSS version 24.

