2.1 Trial design, Procedure and Study Flow

A two-armed parallel RCT following CONSORT statement¹ will be conducted to examine the efficacy of an Internet-based mindfulness-based training (iMBT) to a treatment-as-usual control group (TAU). Intervention (iMBT) will be delivered over a 6-week period via an internet e-learning mental health platform.

All participants who are interested to join this research will be provided with an electronic informed consent form, and online screening. The online screening included a self-assessment of depressive symptoms using PHQ-9 as well as items that assessed the inclusion and exclusion criteria.

Participants will be included if they are: (1) aged over 18, (2) have access to computer and mobile phone, (3) scored > 9 on PHQ-9, administered via telephone by trained interviewers, and (4) have ability to read and type Chinese. Exclusion criteria includes (1) self-reported presence of psychosis or bipolar disorder, post-traumatic stress disorder, drug or alcohol dependence, current use of antipsychotic medications, (2) self-reported frequent suicidal ideation (more than half of the days in the past two weeks), (3) completion of an online mental health program/research for depression in the past 3 months.

Any excluded applicants will receive contact information on community mental health services. Following telephone assessment, eligible participants will be randomized to either iMBT or TAU by block randomization with block number of 6 with allocation ratio of 1:1.

Participants will be assessed at the following time points: (1) before intervention (T0), (2) 2,4 weeks since the commencement of group (T1,2), (3) 6 weeks after (i.e., when the intervention ends) (T3), (4) at 3-month follow-up (T4). Participants in the TAU will have the assessment according to specific times as the iMBT group (i.e. weeks since commencement of group) (see Figure 1).

[figure not shown]

Figure 1 CONSORT flow diagram

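### Significance tests of baseline equivalence cannot show equivalence; describe the T0 scores instead and adjust the T3 and T4 contrasts and Hedges' g for them

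*Protocol*

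**What the plan says.** Section 2.4.1 opens with the baseline comparison: "Significance testing of baseline group equivalence will be conducted using Analysis of variance (ANOVA) and chi square test", with chi-square reserved for nominal variables. It gives no equivalence margin, significance level or list of variables, and no consequence of either result.

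The same section then sets the efficacy analysis: an intention-to-treat linear mixed model for each outcome, with time, group and their interaction as fixed factors. It adds within-group effect sizes from T0 to T3 and from T0 to T4, between-group Hedges' g at T3 and T4, and reliable change on the PHQ-9. It does not say whether the between-group g is computed from raw means or from the model, and it mentions no baseline adjustment for it.

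Section 2.1 specifies "block randomization with block number of 6 with allocation ratio of 1:1". Section 2.3 states that "a sample size of 116 will be needed to detect superiority of the intervention groups over the TAU control group with 80% power", which is 58 per arm.

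**The concern.** A test of difference is given the job of showing sameness. After proper randomisation the null hypothesis of the baseline test is true by design. A significant result is then a false alarm, and a non-significant one says only that the observed difference is small relative to its standard error. What matters for the results is the size of an imbalance and its correlation with the outcome, and a p-value measures neither.

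Two things are at stake. A T0 imbalance that passes the test may be reported as equivalence and then carry into an unadjusted effect size at T3 or T4. In the other direction, a chance p < 0.05 with no stated consequence may cast doubt on a sound randomisation or prompt an unplanned adjustment.

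**Working it through.** **Inputs.** N = 116 and f = 0.11 (section 2.3); 1:1 allocation (section 2.1), so n = 58 per arm; nine instruments listed in the summary of research procedures (Part C, item 4); five mindfulness facets (section 2.4.2). Assumptions, because the protocol does not state them: two-sided alpha of 0.05; all 116 supply T0 data; T0–T3 correlation r between 0.3 and 0.8; equal SDs at T0 and T3.

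**1. The plan's own figure.** A repeated-measures within-between interaction with k = 2 groups, m = 4 measurements ("Both treatment group and control group will be assessed at four different time points") and an assumed correlation of 0.5 uses:
- λ = f²·N·m/(1 − ρ)
- df1 = (k − 1)(m − 1) = 3
- df2 = (N − k)(m − 1)

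This needs N = 114 for 80% power. At N = 116, λ = 0.0121 × 116 × 4/0.5 = 11.2 and power is 0.808. So 116 reproduces to within two participants.

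**2. What the baseline test lets through.**
- The standard error of a standardised difference is √(2/58) = 0.186.
- The largest non-significant observed difference is t(0.975, 114) × 0.186 = 0.368 SD.

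**3. How often chance raises a flag.** For j independent tests the probability of at least one p < 0.05 is 1 − 0.95^j. For correlated test statistics it was simulated with a common correlation.

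| Tests | Independent | Correlation 0.3 | Correlation 0.5 |
|---|---|---|---|
| 9 (instruments) | 37% | 33% | 27% |
| 13 (eight instruments + five facets) | 49% | 42% | 33% |
| 20 (13 + seven further variables, assumed) | 64% | 54% | 42% |

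The range is 27% to 64%.

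**4. What an imbalance does to an unadjusted g.** Given a T0 difference b, the expected T3 difference contains r × b on top of the treatment effect. For b = 0.368:
- r = 0.3: 0.11 SD
- r = 0.5: 0.18 SD
- r = 0.8: 0.29 SD

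This is the most that can pass the test, not the usual case. At one standard error (b = 0.186) the shifts are 0.06, 0.09 and 0.15 SD.

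**5. What adjustment gains.** Relative to a raw T3 comparison (variance 1), a change-from-T0 contrast has variance 2(1 − r) and a baseline-adjusted contrast 1 − r².

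| r | Raw | Change | Adjusted |
|---|---|---|---|
| 0.3 | 1 | 1.40 | 0.91 |
| 0.5 | 1 | 1.00 | 0.75 |
| 0.8 | 1 | 0.40 | 0.36 |

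At r = 0.5, adjustment cuts the variance by 25% against either alternative.

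**The case against.** The strongest reply is that the tests are harmless. The mixed model is fixed whatever they show, and no covariate rule or other decision depends on them. T0 is a level of time, so the time-by-group contrasts compare change from T0. Reliable change is computed within person, and the mediation models work on slopes with a latent intercept. Averaged over randomisations, even a raw g is not biased by baseline imbalance. Whether g is raw or model-based could be settled in an SAP, which is not shown here. All of this stands, and it limits the point to the reporting of baseline data and to the T3 and T4 effect sizes.

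Three stronger readings are tempting, and the protocol does not support them.

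- *The test passes imbalances larger than the planned effect.* This needs f = 0.11 read as d = 2f = 0.22. A two-group comparison at d = 0.22 would need about 650 participants, not 116. Under the interaction design that reproduces 116, with linear divergence over four visits, the interaction SD is 0.186 × D. Then D = 0.11/0.186 = 0.59 SD at T3, which exceeds 0.37 SD.
- *About half of trials will show a false flag.* That takes 13 to 14 independent tests. The protocol gives no number of tests, and scores from related scales are unlikely to be independent.
- *The tests act as permission to interpret unadjusted comparisons.* The protocol does not say so.

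**Conclusion.** The concern holds as a minor point. The protocol fixes a method that cannot deliver the conclusion it is named for. At 58 per arm, observed T0 differences up to about 0.37 SD are non-significant, and at least one chance p < 0.05 is expected in roughly 27% to 64% of trials. The practical exposure is mainly the between-group Hedges' g at T3 and T4. If g is computed raw, the largest imbalance that passes would shift it by about 0.11 to 0.29 SD.

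These figures rest on a two-sided 5% level, complete T0 data on all 116, 9 to 20 tested variables with correlations of 0 to 0.5, and T0–T3 correlations of 0.3 to 0.8. None of these is stated in the protocol. Removing the tests would by itself change no planned estimate; the gain in the results comes from the adjustment.

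**What to change.** In section 2.4.1:

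- Delete the baseline significance tests and the word equivalence. Report T0 means and SDs (counts and percentages for nominal variables) and standardised differences by arm.
- State that no covariate is added or dropped because of that table.
- State that the T3 and T4 group contrasts and the between-group Hedges' g are estimated with adjustment for the T0 score of the same scale. Two ways are T0 as a covariate with the later visits as outcomes, or a common T0 mean for both arms in the mixed model. Name the SD used to standardise g.

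The cost is one sentence replaced and two added. The T0 scores are already collected, so no new data or participants are needed.

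### The efficacy model leaves the T0 means free in each arm and does not otherwise adjust for T0: valid, but precision at T3 and T4 may be given away for nothing

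*Protocol*

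**What the plan says.** Section 2.4.1 plans an analysis of this kind: "intention-to-treat (ITT) linear mixed models using restricted maximum likelihood (REML) estimation will be conducted for each outcome measure". It then lists the mean structure: "Fixed factors of time, group, and time*group will be entered in each model". T0 is evidently one of the levels of time, because the same paragraph says: "Within-group effect size will be computed for pre(T0)-to-post(T3), and pre(T0) to follow-up(T4) changes on each outcome measures". The only between-arm use of baseline in that section is significance testing of group equivalence.

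On the contrast of interest the wording points two ways. H1 in section 1.3 states: "Participants in iMBT group will have greater reduction in depressive symptoms", which is a difference in change from T0. Section 2.4.1 says that between-group effect sizes "will be computed at post(T3) and follow-up(T4"), which reads as a difference at the visit. The primary question in section 1.3 asks about depressive symptoms "relative to a usual care control after the intervention and in 3-month follow-up".

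Two other statements bear on the size of the effect. Section 2.1 requires that participants have "scored > 9 on PHQ-9, administered via telephone by trained interviewers", and section 2.5 expects the trial to finish "with approximately 70% of participants retained".

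**The concern.** A group main effect together with time*group spends a parameter on a T0 difference that randomisation has already set to zero in expectation. The fitted model then offers two estimators at T3 or T4. The raw visit difference takes nothing from a participant's own T0 value when data are complete. The change contrast subtracts T0 with a coefficient of exactly one, whatever the correlation. Neither uses the coefficient that minimises the variance, except by coincidence.

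Which of the two is noisier depends on the correlation, so the protocol cannot know in advance that it has chosen the better one. A contrast that uses the common T0 mean, or conditions on T0, is at least as precise as both, apart from a small cost in degrees of freedom. At stake is the precision of the primary comparison in a trial of 116 people that expects to lose about 30% of them. There is no bias to correct.

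**Working it through.** **Inputs from the protocol.** N = 116, 80% power and f = 0.11 (section 2.3); 1:1 allocation and five occasions, T0 to T4 (section 2.1); about 70% retained (section 2.5).

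**Inputs assumed, because the protocol gives none.** Correlation rho between T0 and the follow-up visit of 0.3, 0.5 or 0.7; SD ratio k = SD(T0)/SD(T3) of 1 or 0.8; a true difference of 0.4 SD at the visit; two-sided alpha 0.05; and a dropout pattern.

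**The plan's own figure.** Treated as a repeated-measures time-by-group interaction with four measurements, correlation 0.5 and alpha 0.05 (all assumed), lambda = 116 × 4 × 0.11² / (1 − 0.5) = 11.23 on 3 and 342 degrees of freedom. Power is 0.808, and the smallest N reaching 80% is 114. So 116 is reproduced closely under these inputs, and nothing below disturbs it. That is a different test from the single-visit contrasts considered next, so their power figures should not be set against the 80%.

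**Variance of the T3 contrast, complete data**, in units of 4 × SD(T3)²/N:
- change from T0: 1 + k² − 2·rho·k
- raw visit difference: 1
- T0-adjusted or common T0 mean: 1 − rho²

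Change minus adjusted is (k − rho)², and raw minus adjusted is rho². Neither can be negative.

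| rho | change (k = 1) | raw | adjusted | cut vs change | cut vs raw | cut vs better of the two |
|---|---|---|---|---|---|---|
| 0.3 | 1.40 | 1.00 | 0.91 | 35% | 9% | 9% |
| 0.5 | 1.00 | 1.00 | 0.75 | 25% | 25% | 25% |
| 0.7 | 0.60 | 1.00 | 0.51 | 15% | 49% | 15% |

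At rho = 0.5 the standard error falls from √(4/116) = 0.186 SD to √(4 × 0.75/116) = 0.161 SD. That is the information of 116/0.75, or about 155 participants.

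**Power at 0.4 SD, N = 116** (noncentral t; 114 df unadjusted, 113 df adjusted), for rho 0.3/0.5/0.7: change 44/57/79%, raw 57/57/57%, adjusted 61/69/85%.

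**Restricted T0 range.** An entry threshold on PHQ-9 may compress the T0 SD. With k = 0.8 the change variance is 1.16/0.84/0.52, so the cut against change is 22/11/2%, and power moves from 51/64/84% to 61/69/85%. The cut against change is zero when k = rho. The cut against raw does not depend on k.

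**With dropout.** Generalised least squares for five occasions, compound symmetry, assumed monotone retention of 100/92.5/85/77.5/70% at T0 to T4, comparing free T0 means with a common T0 mean. For k = 1 and rho 0.3/0.5/0.7:
- T3: cut 30/21/12% against change and 7/21/44% against raw. Power (normal approximation) is 39/50/72% for change and 49/50/53% for raw, against 52/60/77% adjusted.
- T4: cut 28/20/12% against change and 7/20/42% against raw. Power is 37/48/69% for change and 45/48/51% for raw, against 48/57/74% adjusted.

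With k = 0.8 the T3 cut against change is 18/9/2%.

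**Weak T0-to-T4 correlation.** If the correlation halves every six weeks and T4 falls 18 weeks after T0 (assumed), rho at T4 is 0.5³ = 0.125. With complete data and equal SDs the adjusted variance is 1 − 0.125² = 0.98 of raw and (1 + 0.125)/2 = 0.56 of change. Adjustment then gains almost nothing over the raw contrast at T4 but a great deal over change.

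**The case against.** The strongest reply is that nothing is wrong. An ITT REML mixed model with time, group and their interaction is conventional and unbiased, and preferring another is a matter of efficiency. That is correct, and the point is offered only as an improvement. It is not, however, a detail simply left to a later document: the protocol lists the fixed effects, and an analysis plan could bring in T0 only by adding to that list or constraining it.

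Second, the interaction term and H1 both suggest the change contrast, so the large gains against the raw contrast (up to 49%) should carry little weight, and the exact contrast wording could be left to the analysis plan. This has force. Read that way, the relevant range is the one against change: 35% at best among the cases shown with equal SDs and complete data, and 0% when the SD ratio equals rho. The PHQ-9 threshold makes the lower part of that range realistic for the primary outcome. At k = 0.7, for example, the cut is (k − rho)²/(1 + k² − 2·rho·k) = 15/5/0%.

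Third, the fix is not strictly free. An unstructured covariance for five occasions has 15 parameters, while the dropout figures assume a known compound-symmetry covariance. The covariate model adds four slopes for T0 across T1 to T4. These costs are real but small, and the common-mean model has one mean parameter fewer than the planned one. None of this reverses the ordering of the variances.

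**Conclusion.** The concern holds as an efficiency point. The planned model is valid, and the sample size is unaffected. In every case worked through, the T0-adjusted contrast had a variance no larger than that of the change or the raw contrast. The gain against change runs from nothing to about a third among the complete-data cases shown. At a correlation of 0.5 with complete data it is 25% with equal SDs and 11% with the T0 SD at 0.8 of the T3 SD.

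The correlation, SD ratio, effect size, covariance pattern and dropout pattern are all assumptions, so confidence in the actual size is only moderate. The direction is secure. Because T0 PHQ-9 is collected anyway and the change costs little, it should be made.

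**What to change.** State in section 2.4.1 whether the T3 and T4 group contrasts are differences in change or differences at the visit, and bring T0 in through one of two models:

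1. **Common T0 mean.** Keep T0 as an outcome, with categorical time, group-by-time terms for T1 to T4 only, and no group main effect. Use an unstructured covariance, so that a smaller T0 SD is handled. Under this model the change and visit contrasts coincide.
2. **T0 as covariate.** Model T1 to T4 as outcomes, with group, categorical time, group-by-time, T0 and T0-by-time.

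Do not enter T0 as a covariate while it is also an outcome. Take the T3 and T4 PHQ-9 contrasts and the between-group effect sizes from the chosen model, standardising by the raw pooled SD and not the residual SD, so that adjustment does not inflate Hedges' g.

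The cost is a few lines of wording, with the same data, participants and software. Model 1 keeps participants who have only T0 data, which suits the stated ITT aim. Model 2 drops anyone with no post-baseline assessment.
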